5. AMENDMENTS AND UPDATES

Amendment 1: 20JULY2016	
Abstract; 9.2.2. Study Period	Changes: Pre-implementation and post-implementation period dates have been clarified.
	collection, as requested by EMA.
3 Responsible Parties	Change: Principal/Coordinating Investigator has been added.
	Rationale: Investigator has been identified and is now included.
7.2 Background	Change: Dear Healthcare Professional Communication has been changed to Direct Healthcare Professional Communication.
	Rationale: Provides alignment with the definition in GVP Module XV
8.1 Primary Objectives	Change: Details provided for how the primary statistic, (a risk ratio comparing prescriptions' label compliance before vs. after the label change) will be calculated and reported.
	Rationale: Change made in response to EMA request for addition of a comparison between pre- and post-implementation period of risk minimisation measures
9.5 Study Size	Change: An estimate for the number of prescriptions available for study, and a table showing numbers of prescriptions required, have been added
	Rationale: Change made in response to EMA request for a sample size calculation.
9.7 Data Analysis	Change: Description of how the primary endpoint will be calculated has been edited to improve its clarity.
	Rationale: Change made in response to an EMA request to improve the readability of this part of the protocol.
Annex 1, Document 1 List of Companies	Change: Companies have been added, removed, and some company names have been changed.
	Rationale: Reflects companies that have joined and left the Consortium, as well as company name changes that have occurred.
Annex 2, ENCePP Checklist	Change: Page numbers updated
	Rationale: Changes to protocol resulted in changes to page numbers

6. MILESTONES

Milestones	Planned Date		
Start of data collection	Two months after protocol approval		
End of data collection	When data through SEP2015 become available for analysis (estimated as 4Q2016)		
<registration eu="" in="" pas="" register="" the=""></registration>	Before the start of the study		
Final report of study results*	Twelve months after the end of data collection		
*Timing of final report includes the following:			
Data analysis: Three months after data are available			
Final tables available: Two months after data analysis is complete			
Report writing: Three months			
Report review (full Consortium): Four months			

7. RATIONALE AND BACKGROUND

7.1. Introduction

Domperidone, a gastrointestinal motility agent effective in the treatment of acute nausea and vomiting, was first approved in Belgium in March 1978. Currently, single-active-ingredient domperidone is licensed in more than 107 countries, including approximately 25 where it is sold without prescription. In the European Union, domperidone is registered in Austria, Belgium, Bulgaria, Cyprus, Czech Republic, Denmark, Estonia, France, Germany, Greece, Hungary, Ireland, Italy, Latvia, Lithuania, Luxembourg, Malta, The Netherlands, Poland, Portugal, Slovak Republic, Slovenia, Spain, and the United Kingdom.

7.2. Background

In 2011, the EU Pharmacovigilance Working Party (PhVWP) recommended that the product information for domperidone-containing medicines should be updated to reflect the risk of adverse cardiac effects of domperidone including QT prolongation, arrhythmias, and sudden cardiac death, and that domperidone should be used with caution in patients with certain heart conditions, including heart failure, a previous heart attack, angina (chest pains), and heart rhythm disorders. In response to this recommendation, the SmPC was updated in 2012 to include QT prolongation as an adverse drug reaction (ADR).

In March 2013, the EMA PRAC initiated a review of domperidone-containing medicines at the request of the Federal Agency for Medicines and Health Products (FAMHP), under Article 31 of Directive 2001/83/EC over concerns about cardiac adverse effects of domperidone. Subsequently, PRAC recommended that the product label (Summary of Product Characteristics/SmPC and Patient Information Leaflet/PIL) of domperidone-containing medicines should be updated to strengthen the information regarding cardiac risks. In addition, PRAC raised concerns that there may be off-label use of domperidone for the stimulation of lactation in breastfeeding women, for the treatment of

gastro-oesophageal reflux disease (GERD), for the treatment of diabetic and non-diabetic gastroparesis, and for the treatment of symptoms of postural hypotension in Parkinson's patients. More recently the EMA asked that IBS be included in the present study as an off-label indication.

The recommended changes following conclusion of the Article 31 referral included the following:

- restriction of the indication to nausea and vomiting;
- limitation of duration of use to 7 days;
- reduction of the maximum daily dose to 10 mg TID for adults and adolescents (12 years of age and older and weighing 35 kg or more);
- reduction of the maximum daily dose to 0.25 mg/kg TID for neonates, infants, children (less than 12 years of age), and adolescents weighing less than 35 kg;
- contraindication of the combination with other drugs that increase the cardiac risks by themselves or increase the plasma level of domperidone; and
- contraindication in patients with moderate or severe hepatic impairment or certain cardiac conditions.

The CHMP continues to support a positive risk-benefit balance for domperidone provided that the drug is used according to the new label. Within the context of risk minimisation measures, the MAHs distributed a Direct Healthcare Professional Communication (DHPC), and updated the SmPC. PRAC requested that domperidone MAHs perform a drug utilisation study to assess the effectiveness of the above mentioned risk minimisation measures and to monitor the off-label use of the drug. In addition to a physician survey proposed by the MAHs to assess the prescribers' knowledge of the new label of domperidone, EMA suggested the use of a healthcare database as an additional data source to measure domperidone utilisation patterns. This protocol describes a drug utilisation study using healthcare databases in 5 European Union countries.

8. RESEARCH QUESTIONS & OBJECTIVES

The objective of the study is to investigate the effectiveness of risk minimisation measures and describe prescribing patterns of domperidone, including those pertaining to the off-label use of domperidone, in routine clinical practice in selected European Union countries.

8.1. Primary Objectives

To describe the prescribing patterns before and after the changes to the domperidone label and distribution of a DHPC and estimate and compare the overall proportion of domperidone prescriptions before and after implementation of the risk minimisation measures regarding the following measures:

- Composite endpoint consisting of the following components:
 - Maximum daily dose;
 - Duration of use (>7 days);
 - Concomitant medications that prolong the QT-interval or are potent or strong CYP3A4 inhibitors;
 - Prescribing to patients with contraindicated conditions, e.g., moderate or severe liver disease, underlying cardiac diseases; and
 - Prescribing for off-label indications

Domperidone is used as needed, therefore the duration of use may not be the same as the number of days for which domperidone is supplied. As a result, duration of use will be assessed under the following 2 scenarios, which will be likely to bracket the actual (but unknown) situation:

- 1. Domperidone is used only for as little as 1 dose after it is prescribed, and
- 2. Domperidone is used for the entire number of days supplied.

This is intended to bracket the plausible values for duration of use

Primary test statistic: In each country studied, the change in the proportion of all prescriptions that comply with the label based on the above composite endpoint during the 12 months before the label change versus the 12 months after the label change is the primary statistic to be evaluated as a measure of the effectiveness of the label change in that country. The statistic will be evaluated as a risk ratio, i.e., as the ratio of the proportion of prescriptions that met all conditions in the composite endpoint between 1 April 2013 and 31 March 2014 and the proportion of prescriptions that met all conditions of prescriptions that met all conditions in the composite endpoint between 1 October 2014 and 30 September 2015. The point estimate and 95% confidence interval for the above risk ratio will be reported. There are several versions of the composite endpoint are implemented in the databases and the risk ratio (point estimate and 95% confidence interval) will be reported for each. Note that the term "risk ratio" is being used in the sense of a ratio of probabilities (the probability of a prescription being consistent with the new label).

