4. ABSTRACT

Title of Study

A Drug Utilisation Study of Domperidone in Europe Using Databases

Rationale and Background

In March 2013, the European Medicines Agency (EMA) Pharmacovigilance Risk Assessment Committee (PRAC) initiated a review of domperidone-containing medicines at the request of the Federal Agency for Medicines and Health Products (FAMHP), under Article 31 of Directive 2001/83/EC over concerns about cardiac adverse effects of domperidone. Subsequently, PRAC recommended that the product label (Summary of Product Characteristics/SmPC and Patient Information Leaflet/PIL) of domperidone-containing medicines be updated to strengthen the information regarding cardiac risks. In addition, PRAC raised concerns that there may be off-label use of domperidone for the stimulation of lactation in breastfeeding women, for the treatment of gastro-oesophageal reflux disease (GERD), for the treatment of diabetic and non-diabetic gastroparesis, and for the treatment of symptoms of postural hypotension in Parkinson's patients. More recently the EMA asked that inflammatory bowel syndrome (IBS) be included in the present study as an off-label indication.

The recommended changes following conclusion of the Article 31 referral included the following:

- restriction of the indication to nausea and vomiting;
- limitation of duration of use to 7 days;
- reduction of the maximum daily dose to 10 mg TID for adults and adolescents (12 years of age and older and weighing 35 kg or more);
- reduction of the maximum daily dose to 0.25 mg/kg TID for neonates, infants, children (less than 12 years of age), and adolescents weighing less than 35 kg;
- contraindication of the combination with other drugs that increase the cardiac risks by themselves or increase the plasma level of domperidone; and
- contraindication in patients with moderate or severe hepatic impairment or certain cardiac conditions.

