9.3.6. A Composite Endpoint -All Label Requirements

Each prescription will be classified according to whether it appears to violate at least 1 of the above specifications, i.e., has a presumed indication that is off-label, has a dose that is above 30 mg/day (for ages \geq 12 years) or above 0.75 mg/kg/day (for ages <12 years), is written for a patient with a contraindicated condition, or appears to be prescribed concurrently with a medication contraindicated for concurrent use.

To accommodate the 2 areas of uncertainty described above (1] duration of domperidone use and 2] domperidone prescriptions for which the indication is unknown), the above classification will be done in the following 4 ways to reflect the possible combinations of:

- With consideration of days' supply being more than 7 days;
- Without consideration of days' supply being more than 7 days;
- With classifying subjects with an unknown indication as having an off-label indication; and
- Without classifying subjects with an unknown indication as having an off-label indication

This is described in more detail in Section 9.7.

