9.5. Study Size

The study size will vary according to country and data source. All patients available in the study population will be considered for the analysis. Preliminary estimates indicate that the suggested databases capture at least several thousands of domperidone prescriptions in each of the countries being studied.

Review of domperidone sales data for 2015 from IMS and from the CPRD indicates that the number of prescriptions in each of the databases varies by country. The lowest number of prescriptions was observed in the Belgian database, where the count was 22,000.

Table 2 shows the approximate number of prescriptions for a study with the same number of prescriptions in pre-intervention period and the post-intervention to have 90% power to detect, p<0.05 (2-sided test) risk ratios from 1.1 to 1.4 according to the risk during the pre-intervention period. Note that the "risks" are the probabilities of a prescription meeting the label requirements, so a risk ratio of 1.1 represents a 10% improvement in label compliance when comparing the post-intervention period to the pre-intervention period.

Table 2:Approximate number of Subjects Required per Group (Before Intervention, After Intervention) Under Various Scenarios				
"Risk" of complying with label before	"Risk" Ratio =	"Risk" Ratio =	"Risk" Ratio =	"Risk" Ratio =
the intervention period	1.1	1.2	1.3	1.4
10%	16,000	4,500	2,000	1,200
20%	7,200	1,800	900	500
30%	4,000	1,100	500	300
40%	2,700	700	300	200
50%	1700	500	200	100
60%	1200	300	200	100
70%	700	200	100	100
80%	400	100	100	100

Thus, if compliance with the new label requirements as low as 10% in the pre-intervention period, the study will have \geq 90% power to detect even a risk ratio of 1.1 (a 10% improvement), and smaller improvements would be of limited public health interest. If compliance with the new label is higher than 10% in the pre-intervention period, the study will have \geq 90% power to detect smaller improvements in compliance with the new label. All domperidone prescriptions that are captured during the study period and meet the inclusion criteria will be included in data analysis.

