9.7. Data Analysis

Data analysis in the study will be descriptive. Continuous variables will be presented using appropriate descriptive statistics, such as mean, median, standard deviation and range. Categorical variables will be presented using percent and frequency tables. The rates and 95% CI of all study endpoints (i.e., risk minimisation indicators) will be calculated for the 2011-2015 period, using quarterly time blocks for the pre- and post- risk minimisation implementation periods. The rates will be calculated per 1000 domperidone-treated patients or as percentage of domperidone prescriptions, as appropriate. Paediatric data will be described separately from adult patients and rate of paediatric use will be calculated as fraction of overall domperidone utilisation. Missing values will be reported as missing and no imputation will be undertaken. All data analysis will be done in SAS using the version that is current when the analyses are done.

The rates for the primary endpoints of the study (the proportion of all prescriptions that are consistent with the revised label) will be calculated 4 ways to address uncertainty about 1) Unknown indication (is it assumed to be nausea and vomiting and therefore on-label, or is it assumed to be some other indication and therefore off-label) and 2) Duration of use that may be shorter than the days' supply (prescriptions with more than 7 days' supply assumed to

be intended for ≤ 7 days use, and provision of additional tablets for possible future episodes, and therefore on-label, versus assumed to be for >7 days use and therefore off –label):

- 1. Unknown indication assumed to be nausea and vomiting. Duration assumed to be ≤ 7 days (most optimistic scenario) meets the following conditions:
 - a. Prescription for nausea and vomiting or unknown indication but no recent diagnosis of GERD, gastroparesis, IBS, symptoms of postural hypotension in Parkinson patients, or as an aid to lactation;
 - b. Dose no higher than recommended;
 - c. No prescription to patients with certain cardiac and hepatic conditions; and
 - d. No co-prescription with CYP3A4 inhibitors or QT-prolonging drugs. (This considers such contraindicated co-medications only when they were prescribed ≤ the date of the domperidone prescription.)
- 2. Unknown indication assumed to be an off-label indication, duration assumed to be \leq 7days (an intermediate scenario) meets the following conditions:

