9.9. Limitations of the Research Methods

9.9.1. Strengths

- The study will use longitudinal real-life data on the utilisation of domperidone in different European countries with a pre- and post- study design to measure the effectiveness of the risk minimisation activities and examine changes on prescribing patterns. Data on prescription patterns prior to the label change provide a useful comparator for the prescription patterns observed after the label change.
- The data from this study are not collected by specific consent of patients or prescribers and thus are not subject to volunteer and reporting bias.
- All prescriptions for eligible patients that are captured by the database will be included, providing a robust sample size and a statistically-reliable estimate of compliance with the new domperidone label.
- Data on prescription patterns prior to the label change provide a useful comparator for the prescription patterns observed after the label change and distribution of the DHPC. Thus this study provides an opportunity to demonstrate not only the final outcomes of the implemented risk minimisation measures, but also to demonstrate the effectiveness of the implementation process by comparing the endpoints "before" and "after" the implementation.
- Using the combination of the prescribers' survey and healthcare database analysis, the extent of domperidone on-label vs. off-label prescription will be assessed both in terms of process indicators (investigated through survey) and outcome indicators (investigated through database analysis). This should provide a comprehensive view of the effectiveness of domperidone risk minimisation measures.

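### The primary risk ratio counts every prescription equally, so a change in prescriptions per continuing patient can move it in either direction without any change in what is prescribed to whom

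*Protocol*

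**What the plan says.** Section 8.1 evaluates, in each country, "the change in the proportion of all prescriptions that comply with the label based on the above composite endpoint" as a risk ratio between 1 April 2013 to 31 March 2014 and 1 October 2014 to 30 September 2015. It explains the ratio in terms of "the probability of a prescription being consistent with the new label".

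Repeats count separately. Section 9.5 states: "All domperidone prescriptions that are captured during the study period and meet the inclusion criteria will be included in data analysis". Section 9.9.1 presents this as a strength: "All prescriptions for eligible patients that are captured by the database will be included".

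The label changes under evaluation include "limitation of duration of use to 7 days" (Abstract; also 7.2). The composite is scored in four versions (9.3.6, 9.7). Versions 1 and 2 are scored "Without consideration of days' supply being more than 7 days"; versions 3 and 4 "With consideration of days' supply being more than 7 days". All four use the prescription as the unit.

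A patient denominator appears once, in 9.7: "The rates will be calculated per 1000 domperidone-treated patients or as percentage of domperidone prescriptions, as appropriate". It is assigned to no endpoint, and the same section then defines the primary endpoint on prescriptions. Section 9.2.1 defines an index date as the first prescription, but the primary statistic does not use it.

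**The concern.** A prescription-weighted proportion depends on two things: how compliant each kind of user is, and how many scripts each kind generates. The second would do no harm if it were stable between the windows. Here it may not be, because the natural way to act on a 7-day limit for a patient who continues treatment is to write shorter scripts more often. The same treatment then yields more scored units after the label change than before.

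The ratio is to be read as a measure of the effectiveness of the label change. If it also carries a change in scripts per patient, a country could appear to worsen because prescribers moved towards the limit, or be credited with an improvement that is only re-weighting. Nothing planned would separate the two. The four versions vary only the handling of unknown indication and days' supply, the tabulation of days supplied shows script length but not scripts per patient, and 9.9.2 does not list the issue.

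**Working it through.** **Yardstick.** The protocol has no figure for scripts per patient, so there is nothing of its own to reproduce on this point. The benchmark is the risk ratio of 1.1 in 9.5, below which improvements are said to be of limited public health interest. Ratios here are post over pre, as in 9.5. The downward mirror of 1.1 is 1/1.1 = 0.91.

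**Route 1: re-weighting (versions 1 and 2, days' supply ignored).** Let A be one-off patients with one script each and compliance a. Let C be continuing patients with s scripts a year and compliance c.

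P(s) = (A·a + C·s·c) / (A + C·s), and RR = P(s after) / P(s before).

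All values are assumptions: A = 100, C = 5, s before = 13 (365/28 ≈ 13). Afterwards s = 52 (every 28-day script becomes four 7-day scripts), 26 (one third of them split, since 13 × (1 + 3 × 1/3) = 26) or 17 (about one tenth split, since 4/39 ≈ 0.10).

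At a = 80%, c = 40%:
- before: (80 + 26)/165 = 64.2%
- s = 52: (80 + 104)/360 = 51.1%, RR 0.80
- s = 26: (80 + 52)/230 = 57.4%, RR 0.89
- s = 17: (80 + 34)/185 = 61.6%, RR 0.96

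The other cases use the same formula:

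| Compliance, one-off / continuing | before | RR, s = 52 | RR, s = 26 | RR, s = 17 |
|---|---|---|---|---|
| 80% / 40% | 64.2% | 0.80 | 0.89 | 0.96 |
| 40% / 80% | 55.8% | 1.24 | 1.12 | 1.05 |
| 100% / 0% (extreme) | 60.6% | 0.46 | 0.72 | 0.89 |
| equal | same | 1.00 | 1.00 | 1.00 |

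Weighting each patient once in the 80%/40% case gives (80 + 2)/105 = 78.1% in both windows, RR 1.00. If compliance truly rose by 10% in both groups while s went from 13 to 26, the prescription ratio would read 1.1 × 0.893 = 0.98.

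A second set of assumptions points the same way. Take 5% to 30% continuing users with 3 to 12 long scripts a year, and either 25% to 100% of these split into four or half of them split into two. The ratio runs from about 0.80 to 0.97 at 80%/40%, and from 1.03 to 1.26 at 40%/80%.

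**Route 2: the nausea look-back in 9.3.2 (version 2).** An on-label indication needs a nausea or vomiting code on the prescription day or in the 7 days before. Take one code on day 0 and no other relevant diagnosis.
- One 28-day script on day 0: nausea, 1 of 1 on-label.
- Four 7-day scripts on days 0, 7, 14 and 21: the first two are nausea and the last two unknown. Version 2 scores unknown as off-label, so 2 of 4.

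This route needs no difference between types of patient. Version 1 is unaffected, because it scores unknown as on-label.

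**Versions 3 and 4.** A supply of 7 days or less is itself a criterion here, so some movement is intended, but its weight is inflated. Assume 10% continuing users with 6 long scripts a year, 80% compliance on everything else in both groups, and half of the continuing patients moved to four short scripts for each long one.
- By prescription: before 0.72/1.5 = 48%; after (0.72 + 0.96)/2.4 = 70%; RR 1.46.
- By patient: before 72%; after 72% + 10% × 0.5 × 80% = 76%; RR 1.06.

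**The case against.** The prescription is a defensible unit. The objective concerns prescribing patterns, 8.1 says openly that the ratio is a probability per prescription, and each off-label repeat is a further decision against the label. That stands, and it is why the primary ratio should be kept.

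A reader might infer that the ratio must move by construction. The documents do not support this. The measure limits duration of use; it is not a rule on script length, and 9.7 expressly allows that a longer supply may be meant for short use with tablets kept for later episodes. Prescribers may also stop treatment. In a mix of 10% continuing users with 6 scripts a year at 80%/40%, losing half of the continuing scripts gives 0.84/1.2 = 70% against 64%, RR 1.09, which is a real change in prescribing. Route 1 needs both splitting and unequal compliance, and the protocol gives neither.

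A reader might also take 0.46 as the likely size, or expect a fall in all four versions. The first needs one-off users fully compliant, continuing users never compliant, and every script split. The second needs a violation on every repeat. Under 9.3.2 an off-label indication requires a listed diagnosis in the preceding 2 months; without one the script becomes unknown, which versions 1 and 3 score as on-label.

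Finally, components and days supplied are reported separately, and an analysis plan that is not shown may add patient-level sensitivity analyses. The separate tables would reveal shorter scripts, but not how far these moved the primary ratio. The unit of that ratio is fixed in the protocol itself.

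**Conclusion.** The point holds as a possibility that the primary statistic leaves unguarded, not as a demonstrated bias. The prescription-weighted ratio can move in either direction through scripts per patient alone. Direction and size cannot be derived from the protocol. Under the moderate 80%/40% assumption, splitting a third or more of long scripts shifts the ratio past the mirror of the protocol's own 1.1, while splitting a tenth does not. With equal compliance, route 1 contributes nothing. Route 2 follows from the protocol's own window, but it bears on version 2 and only where long scripts are split. In versions 3 and 4 part of the movement is a genuine label gain that is over-weighted. Because the size is unknown and can be measured from the planned extract, it should be measured.

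**What to change.** Keep the per-prescription ratio as primary. In 8.1, add for each version and country:
- a patient-level ratio with 95% CI, either weighting each patient once per 12-month window or using the first prescription in each window;
- the mean number of prescriptions per patient in each window.

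Where the two ratios differ materially, establish how much of the difference comes from prescription frequency before drawing an effectiveness conclusion. A rule that allows a conclusion only when both ratios point the same way is not advised: it is undefined when the patient-level ratio is 1.00. Add the issue to 9.9.2.

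The two patient-level forms differ. Weighting each patient once removes route 1 but not route 2, since the patient in that example still falls from 1 to 0.5. The first-prescription form largely avoids both, but it does not register changes in repeat prescribing, and in versions 3 and 4 it still passes the first of a weekly series.

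The cost is one more ratio per version and country and one descriptive row per window, all from the same extract.

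### Section 9.5 sizes the study as if prescriptions were independent subjects, so its unconditional claim of at least 90% power at 10% compliance and risk ratio 1.1 tolerates a net design effect of only 1.11

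*Protocol*

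**What the plan says.** Protocol 8.1 makes the prescription the unit of analysis. The primary statistic in each country is "the change in the proportion of all prescriptions that comply with the label", expressed as a risk ratio between two 12-month periods with a 95% confidence interval. Section 9.2.1 admits any patient with one or more prescriptions, 9.3.6 classifies each prescription separately, and 9.9.1 confirms that "All prescriptions for eligible patients that are captured by the database will be included".

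Section 9.5 describes Table 2 as the size needed for "a study with the same number of prescriptions in pre-intervention period and the post-intervention", "to have 90% power to detect", at "p<0.05 (2-sided test) risk ratios from 1.1 to 1.4". The table title, however, reads "Approximate number of Subjects Required per Group". The smallest database is Belgium, with 22,000 prescriptions. The Table 2 entry for 10% compliance and risk ratio 1.1 is 16,000, and the section concludes that the study has at least "90% power to detect even a risk ratio of 1.1" in that case. It mentions no design effect, intraclass correlation, prescriptions per patient, or clustering by patient or practice.

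**The concern.** A patient who receives several prescriptions in a period contributes several correlated outcomes. Part of the correlation follows from the endpoint definitions. In 9.3.4 a hepatic diagnosis flags every later prescription back to January 2011 and a heart failure diagnosis flags six months. In 9.3.2 an off-label diagnosis applies for two months, unless nausea or vomiting was recorded in the last week. Prescriptions from one practice may also resemble each other. Positive correlation within a period means that 22,000 prescriptions carry less information than 22,000 independent subjects.

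Two things are at stake. The first is the power guarantee, which Amendment 1 added because the regulator asked for a sample size calculation. The second is the width of the interval around each country's risk ratio, which is the main evidence on whether the label change worked. If the interval were computed as for independent observations while net clustering was present, chance variation could be read as improvement or deterioration.

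**Working it through.** **Inputs from Protocol 9.5:** two-sided 5% test, 90% power, equal numbers before and after, 10% compliance before, and risk ratio 1.1 ("so a risk ratio of 1.1 represents a 10% improvement in label compliance"), hence 11% after. The available number is 22,000. I take it as the usable count in each period. That is an assumption: it is a 2015 count, no figure is given for the earlier period, and no reduction is stated for the 180-day history criterion.

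**Step 1. Reproduce the tabulated figure.** For independent observations with pooled variance under the null:

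n = [z(α)·√(2·p̄·(1−p̄)) + z(β)·√(p1(1−p1) + p2(1−p2))]² / (p2−p1)²

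With p1 = 0.10, p2 = 0.11 and p̄ = 0.105, the two roots are 0.43353 and 0.43347.

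- Two-sided: (1.960 × 0.43353 + 1.2816 × 0.43347)² / 0.01² = 19,747.
- One-sided: (1.645 × 0.43353 + 1.2816 × 0.43347)² / 0.01² = 16,094.

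The tabulated 16,000 is not reproduced two-sided. A continuity correction (19,947), unpooled variance (19,744) and a log risk ratio (19,769) do not bring it closer. At 16,000 per group two-sided power is 83.1%. Most of the table shows the same pattern. In the risk ratio 1.1 column:

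| Compliance before | Table 2 | Two-sided | One-sided |
|---|---|---|---|
| 10% | 16,000 | 19,747 | 16,094 |
| 20% | 7,200 | 8,714 | 7,102 |
| 30% | 4,000 | 5,037 | 4,105 |
| 50% | 1,700 | 2,095 | 1,707 |

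A few small cells fit neither version closely (60% with risk ratio 1.3: tabulated 200, two-sided 137, one-sided 112).

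**Step 2. Margin.** The table suggests slack of 22,000 / 16,000 = 1.375. Under the stated two-sided test it is 22,000 / 19,747 = 1.11. With independence, 22,000 per period still gives 92.8%, so the one-sided slip alone does not overturn the conclusion.

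**Step 3. Power by net design effect (DE).** Effective n = 22,000 / DE, two-sided, risk ratio 1.1. The last column is the coverage of a nominal 95% interval that ignores clustering, 2Φ(1.96/√DE) − 1.

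| Net DE | Power, 10% before | Power, 20% before | Coverage if ignored |
|---|---|---|---|
| 1 | 92.8% | 99.9% | 95% |
| 1.5 | 79.8% | 98.8% | 89% |
| 2 | 67.7% | 95.4% | 83% |
| 3 | 50.6% | 84.5% | 74% |

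**Step 4. What could produce these values.** The protocol gives neither m (prescriptions per patient per period) nor the ICC, so these are assumptions, with DE = 1 + (m − 1) × ICC:

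- m = 1.5, ICC 0.2: DE 1.10, power 90.4%.
- m = 1.5, ICC 0.3: DE 1.15, power 89.1%.
- m = 2, ICC 0.5: DE 1.5, power 79.8%; 29,621 needed.
- m = 3, ICC 0.5: DE 2.0, power 67.7%; 39,494 needed.
- m = 5, ICC 0.5: DE 3.0, power 50.6%; 59,241 needed.

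**Step 5. Offset from patients seen in both periods.** If the two period proportions have correlation ρ, net DE = DE × (1 − ρ). With DE 1.5 and ρ = 0.3 it is 1.05 and power is 91.6%. With DE 2 and ρ = 0.3 it is 1.4 and power is 82.4%. In simulation (assumed geometric number of prescriptions with mean 2, ICC 0.5, 600 runs) the variance was about 2.0 times the independence value with no overlap, and about 1.4 times with half the patients in both periods.

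**Step 6. Where the fragility lies.** Tolerated DE with 22,000 per period is 1.11 at 10% and risk ratio 1.1, but 22,000 / 8,714 = 2.52 at 20%, 22,000 / 5,037 = 4.37 at 30%, and 22,000 / 5,142 = 4.28 at 10% with risk ratio 1.2.

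**The case against.** A reader might infer that the reported 95% interval is invalid. The documents do not support that. Sections 8.1 and 9.7 name no variance method, and the statistical analysis plan that 9.8 mentions is not at hand; it may already use a clustered variance. Only the conditional statement stands: a conventional two-proportion interval would be too narrow if the net design effect exceeds 1.

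A reader might also infer that 90% power is not delivered. That is not shown either. It depends on prescriptions per patient, ICC and overlap, none of which is given; with m = 1.5 and ICC 0.2, or with DE 1.5 and ρ = 0.3, power stays above 90%. Several endpoint components are also tied to short windows around each prescription (seven days for nausea and vomiting, 30 days for hypokalaemia, co-medication at the prescription date), which may lower the within-patient correlation.

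Further, 10% is a lower-end case, Belgium is the smallest database, all available data are used whatever the power, the analysis is called descriptive, and the ENCePP checklist says that no formal hypothesis is tested. All of this is fair and limits the consequence. It does not remove the point. Section 9.5 chose this very case for its guarantee and attached no condition. The guarantee rests on a subjects table set against a prescription count, and that calculation belongs to the protocol, not to a later plan.

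**Conclusion.** The point holds in conditional form. The statement of at least 90% power at 10% compliance and risk ratio 1.1 is not supported by the calculation behind it. Two-sided, it needs about 19,750 independent prescriptions per period, not 16,000, and 22,000 leaves room for a net design effect of 1.11. Under assumed net design effects of 1.5, 2 and 3, power is about 80%, 68% and 51%.

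The possible shortfall concerns low compliance with a risk ratio of 1.1 in the smallest database. It matters most for the strictest of the four composite versions in 9.7, where low compliance is most plausible. At 20% compliance the design effect would have to exceed about 2.5 before power fell below 90%. These results assume 22,000 usable prescriptions in each period; fewer would narrow the margin.

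**What to change.** - **Section 9.5, table:** title Table 2 as prescriptions per period under independence and recompute it for the stated two-sided test. Leave blank the 80% row at risk ratios 1.3 and 1.4, where compliance would exceed 100% (0.8 × 1.3 = 1.04; 0.8 × 1.4 = 1.12).
- **Section 9.5, power statement:** replace the unconditional claim with power at net design effects from 1 to about 3, and state the assumed prescriptions per patient, ICC and overlap between periods.
- **Sections 8.1 and 9.7:** estimate the risk ratio with a log-binomial or modified Poisson model on period, with sandwich variance clustered on practice, or on patient where no practice identifier exists. Patients or practices present in both periods must keep one cluster identifier, so that the offset is counted. Add a sensitivity analysis using the first eligible prescription per patient per period.

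The cost is wording and standard SAS procedures, with no change to data extraction. The downside is probably wider intervals than a conventional calculation would give, and a less favourable stated power.
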